6.6.3 PK parameters

6.7 BASELINE, TIME WINDOWS, AND CALCULATED VISITS

6.7.1 Baseline

The last measurement observed prior to start of trial medication will be assigned to baseline. Note that for some trial procedures (for example body weight, vital signs, laboratory tests) this may be the value measured on the same day trial medication was started. In these cases it will be assumed that the measurements were taken prior to the intake of any study medication. For tumour assessment, baseline evaluations must be based on Magnetic Resonance Imaging (MRI) or Computed Tomography scans performed no more than 28 days prior to start of trial medication.

Study days and visits will be labelled according to the flow chart of the CTP.

Unless otherwise specified, baseline is defined as the latest time-point before the very first administration of any study medication. If this criterion is not fulfilled then no baseline will be derived.

Laboratory values:

Baseline is defined as the latest time-point before the very first administration of any study medication. For laboratory values where not only the examination date but also time are recorded, examination time has to be taken into account when defining baseline. That is, a laboratory value on the same date as the first study drug administration is considered as baseline value if and only if the recording time was before or the same as the time of first study drug administration.

If any of these times are missing and the date of laboratory value is equal to the date of first study drug administration, then the laboratory assessment will be considered as according to protocol, i.e. as prior to first study medication.

6.7.2 Time windows for every RECIST assessment

In order to identify whether consecutive imaging time-points are missing for a given patient, a nominal time point [6, 12, 18 weeks and every 9 weeks thereafter] will be assigned to each and every image. This is achieved by creating windows for every RECIST assessment. The windows are defined in Table 6.7.2: 1 below.

Table 6.7.2: 1

Nominal time-points and windows for imaging

Nominal time-point [weeks from start of therapy]	Due date of scans [days]	Window [days]
6	43	1 to =< 64
12	85	65 to =< 106

Proprietary confidential information © 2018 Boehringer Ingelheim International GmbH or one or more of its affiliated companies

Table 6.7.2: 1(continued) Nominal time-points and windows for imaging

Nominal time-point [weeks from start of therapy]	Due date of scans [days]	Window [days]
18	127	107 to =< 158
27	190	159 to =< 221
Every 9 weeks interval	*	*

*Due date of imaging = (nominal time point * 7) + 1. To calculate the lower bound of the window, use the middle point between the due date of the previous time point and the current due date+1. To calculate the upper bound of the window, use the middle point between the due date of the next time point and the current due date.

If a patient does not have an image in one of the windows described above, he/she will be said to have 'missed an assessment' for that time-point. In case a patient has more than one assessment in one window, the assessment with the latest outcome will be used for the analysis unless a PD has been recorded earlier then PD will be used.

Proprietary confidential information © 2018 Boehringer Ingelheim International GmbH or one or more of its affiliated companies

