Duration of treatment: 
One treatment cycle consists of 21 days without discontinuation of study treatment.The study treatment may be continued until patients meet any of the criteria for discontinuation.				

Proprietary confidential information © 2024 Boehringer Ingelheim International GmbH or one or more of its affiliated companies

Name of company:		Tabulated Trial Protocol	
Boehringer Ingelheim			
Name of finished product:			
Not applicable			
Name of active ingredient:			
Xentuzumab (BI 836845)			
Protocol date:	Trial number:		Revision date:
28 Feb 2014	1280.15		29 Apr 2022
Criteria for efficacy:	The following assessments will be performed according to Response Evaluation Criteria in Solid Tumours (RECIST) version 1.1 as other efficacy assessments 
• Objective response: number of patients whose best response is either complete response (CR) or partial response (PR)• Disease control: number of patients whose best response is either CR, PR, or stable disease (SD)• Duration of disease control: time from first disease control (CR, PR, or SD) to the time to progression or death		
Criteria for pharmacokinetics:	Pharmacokinetic profile of BI 836845		
Criteria for safety:	The following adverse events will mainly be evaluated according to Common Terminology Criteria for Adverse Events version 4.03 The primary endpoint: 
• MTD of BI 836845 in Japanese patients with advanced solid tumours (as identified by the number of patients with dose-limiting toxicities [DLTs]) Other safety assessments: 
• All adverse events• Laboratory tests• Eastern Cooperative Oncology Group (ECOG) performance status• Vital signs• Twelve (12)-lead electrocardiogram (ECG)		
Statistical methods:	Descriptive statistics		

FLOW CHART

Study period	Screening	Treatment ^a					
		Cycle 1			Cycle 2		
Visit	-28 to -1	1	2	3	1	2	3
Day (day range)		1 (±1)	8 (±1)	15 (±1)	1 ^b (±2)	8 (±2)	15 (±2)
Informed consent	X ¹				X ²		
Demographics	X						
Medical history	X						
Inclusion and exclusion criteria	X	X ³					
Physical examination	X	X			X		
Vital signs ⁴	X	X	X	X	X	X	X
Body height	X						
Body weight	X				X		
ECOG performance status	X				X		
Pregnancy test ⁵	X						
Tumour assessment (RECIST) ⁶	X ⁷						
Clinical tumour assessment	X				X		
Tumour markers ⁸	X				X		
Twelve (12)-lead ECG ⁹	X	X		X	X		
ECHO or MUGA ¹⁰	X						

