- e. At the time of all patients in the trial having sufficient data to answer the primary endpoint (see [Section 5.2.1](#)), patients continuing on study treatment will have the EOT assessments (except for blood collection for biomarker analyses) performed and then continue on study treatment into the rollover part with reduced clinical data collection.
- f. The first follow-up (FU1) visit must be performed on 42 (a window of +7) days after the last administration of BI 836845.
- g. The second follow-up (FU2) visit may be performed on 28 (a window of ±4) days after FU1 visit over the telephone if a visit at the trial site cannot be arranged. The visit will be skipped for patients conducted the rollover part.

- 1. Written informed consent must be obtained before any assessment at screening.
- 2. For patients who are willing to continue the study treatment after completion of Cycle 1, written informed re-consent must be obtained before study treatment on Visit 1 of Cycle 2.
- 3. The investigator confirms whether inclusion and exclusion criteria are still valid or not.
- 4. On administration day of every cycle, vital signs are performed at pre-infusion, during infusion (30 ± 5 minutes after start of infusion), and immediately before end of infusion. Further vital signs to be taken at any time if clinically indicated and/or after discontinuation of study treatment.
- 5. For women of child bearing potential, serum beta-human chorionic gonadotropin (β-hCG) is evaluated for pregnancy test at screening (within 7 days before start of study treatment), Visit 1 of every odd cycle, and EOT visit.
- 6. Tumour assessment is performed according to RECIST criteria version 1.1 by CT or MRI imaging at screening, end of Cycle 2 (before start of Cycle 3), end of Cycle 4 (before start of Cycle 5), and end of Cycle 6 (before start of Cycle 7). Thereafter, tumour assessment may be conducted every 3 cycles before start of Cycles 10, 13, 16, etc. Imaging may be performed within 7 days before start of the respective treatment cycle. The same radiographic procedure should be used throughout the cycle of trial. Tumour assessment may also be performed if the investigator considers it should be performed from the result of clinical tumour assessment.

Proprietary confidential information © 2024 Boehringer Ingelheim International GmbH or one or more of its affiliated companies

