7.2 NULL AND ALTERNATIVE HYPOTHESES

The analyses in this trial are descriptive and exploratory. No formal statistical tests will be performed.

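### SAP 6.7.2 keeps the latest scan in each imaging window and protects only an earlier PD, so read literally a CR or PR can be replaced by a later SD or NE although the protocol counts best response

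*SAP*

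**What the plan says.** SAP 6.7.2 gives detection of missed consecutive imaging time points as the reason for the windows. To that end, "a nominal time point [6, 12, 18 weeks and every 9 weeks thereafter] will be assigned to each and every image". Table 6.7.2: 1 lists the windows, and its footnote gives the construction rule. A patient with no image in a window has missed that assessment.

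The section then adds a rule for windows that hold more than one scan: "In case a patient has more than one assessment in one window, the assessment with the latest outcome will be used for the analysis". The sentence continues with one exception: if a PD was recorded earlier, PD is used. No similar protection is given to an earlier CR or PR, and nothing in the visible text confines the rule to the missed-scan check.

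The protocol synopsis defines the efficacy counts differently: "Objective response: number of patients whose best response is either complete response (CR) or partial response (PR"). Disease control is likewise a count by best response, with SD added.

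On scan timing, Flow Chart footnote 6 says: "Imaging may be performed within 7 days before start of the respective treatment cycle". The same footnote allows extra scans at the investigator's judgement. The Flow Chart also marks a RECIST assessment at EOT, and footnote e requires the EOT assessments (apart from biomarker blood) before a patient enters rollover.

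**The concern.** A latest-value rule and a best-value endpoint give different answers whenever a patient's later scan in a window is worse than the earlier one. The rule was written for a bookkeeping purpose, but its wording reaches the analysis itself. A programmer who applies it before deriving best response would drop a CR or PR that was followed in the same window by SD or NE, without any warning in the output.

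At stake are the objective response count and, when NE does the replacing, the disease control count. Protocol 2.2 names efficacy among the data that may support a relevant biological dose if no MTD is identified. With so few patients, one reclassification is visible in the reported result.

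**Working it through.** **1. Reproduce the windows.** Inputs are the nominal weeks and the footnote to Table 6.7.2: 1. The due date follows "Due date of imaging = (nominal time point * 7) + 1". The footnote's upper-bound rule begins "To calculate the upper bound of the window, use the middle point between the due date of the next time point and the current due"; I take it as the midpoint of adjacent due days, rounded down. Each lower bound is then the previous upper bound plus 1. Scheduled scan days come from Flow Chart footnote 6 (up to 7 days before cycle start), with the ±2 days of footnote c in brackets.

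| Week | Due day | Midpoint to next due day | Window | Length (days) | Scheduled scan days |
|---|---|---|---|---|---|
| 6 | 6×7+1 = 43 | (43+85)/2 = 64 | 1–64 | 64 | 36–43 (34–45) |
| 12 | 12×7+1 = 85 | (85+127)/2 = 106 | 65–106 | 42 | 78–85 (76–87) |
| 18 | 18×7+1 = 127 | (127+190)/2 = 158.5 | 107–158 | 52 | 120–127 (118–129) |
| 27 | 27×7+1 = 190 | (190+253)/2 = 221.5 | 159–221 | 63 | 183–190 (181–192) |

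Every due day and upper bound in the SAP table is reproduced, as is every lower bound from week 12 on. Day 1 for week 6 is set by the table and not by a midpoint. From week 27 on, the windows are 63 days long.

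**2. Can a window hold two scans?** Scheduled scans fall one per window, so a second scan needs one of three sources:

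- The EOT scan, within 5 days of stopping and so possible on any study day. If stopping falls on a scheduled visit, the EOT visit replaces that visit.
- The EOT assessments before rollover, timed by trial progress and not by the patient's own scan schedule. The last entry in the SAP history table is dated 10-Dec-18. Rollover came with the protocol amendment of 04 Jul 2019, so the supplied SAP predates this source.
- An unscheduled scan at the investigator's judgement.

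**3. Apply the rule literally** (PD if any is recorded, otherwise the last value) and compare it with the better of the two readings up to PD.

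| Scans in one window | Value kept | Best up to PD |
|---|---|---|
| PR, SD | SD | PR |
| PR, NE | NE | PR |
| SD, NE | NE | SD |
| CR, PR | PR | CR |
| PR, PD | PD | PR |
| SD, PR | PR | PR |
| PD, PR | PD | PD |

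Objective response changes in rows 1, 2 and 5. Disease control changes when NE replaces an evaluable reading (rows 2 and 3) and in row 5. CR then PR changes the category but not the response count.

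Example: PR on Day 42, treatment stopped for an adverse event, EOT scan on Day 58 read as SD. Both days lie in the window for Days 1–64, so the week-6 value is SD. The response is lost from the count only if no other window shows a CR or PR.

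**4. Size if it happens.** One patient is 1/6 = 16.7% of a six-patient cohort and 1/24 = 4.2% of the maximum enrolment. For scale, protocol 1.4 reports 2 PRs among 81 patients in the two earlier phase I trials, both among the 48 in the weekly-schedule trial. If those rates carried over (an assumption), 24 patients would yield 24×2/81 = 0.59 to 24×2/48 = 1.0 responses. This is the number of responses at stake, not the number lost. The documents give no basis for the probability of a second, worse, non-PD scan in the same window.

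**The case against.** The strongest reply is that the deciding text is not public. The SAP's efficacy definitions and protocol 5.1.1, 5.1.2 and 7.3.2 are not shown, nor is the consecutive-missed-scan rule that the windows were built for. A hidden section may derive best response from all scans and may set a minimum duration for SD. This stands: actual loss of a response cannot be claimed. It does not remove the conflict in the visible text, because 6.7.2 nowhere says that its selection rule stops short of best response.

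It is also fair that the trigger is narrow, since scheduled scans never share a window. The stakes are limited too. Protocol 7.2 says: "The analyses in this trial are descriptive and exploratory. No formal statistical tests will be performed". Efficacy is listed as an other assessment, it would be weighed with safety, pharmacokinetics and pharmacodynamics in any biological-dose recommendation, and the sponsor has since ended oncology development of the drug (protocol 2.3). All of this bears on importance, not on whether the rule is worded correctly.

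A reader might also infer that starting the week-6 window at Day 1 inflates disease control by turning a very early SD scan into week-6 SD. The documents do not support this. Under the synopsis, a best response of SD counts whatever time-point label the scan carries. Any such effect would come from the endpoint definition or from a minimum SD duration that may be in unseen text. Nor can Day 36 serve as the earliest creditable day for SD: Cycle 3 may start on Day 41 (43−2), and imaging 7 days earlier falls on Day 34, which is still on schedule.

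**Conclusion.** The point holds as a conflict between a stated rule and a stated endpoint. Within a window of 42 to 64 days, SAP 6.7.2 lets a later SD or NE replace an earlier CR or PR, while the protocol counts responders by best response. If the rule feeds best response, the bias in objective response is downward. Each affected patient costs one responder: 16.7 percentage points of a six-patient cohort, or 4.2 points of 24.

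This rests on three assumptions: the closing sentence of 6.7.2 is applied as written, no unseen rule overrides it, and the patient shows no CR or PR in another window. How often these would coincide is not established. It would be too strong to say that the reported response or disease control figures are biased. The primary MTD endpoint, which depends on DLTs in Cycle 1, is unaffected.

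**What to change.** In SAP 6.7.2, state that the windows serve only to identify missed assessments, and that best response is derived from all post-baseline assessments up to PD or new anti-cancer therapy.

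If the programs need one value per window, replace the latest-scan rule with this order: PD if present, otherwise the best evaluable response in the window, with NE never replacing an evaluable result. The first option is cleaner, because the second still drops a response that precedes PD in the same window.

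Align any other response rule in the SAP with whichever option is chosen. No change to the window bounds and no SD day cutoff is needed for this point. The cost is a few sentences and minor reprogramming, with no effect on data collection or on the primary endpoint.

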7 PLANNED ANALYSES

The labelling and display format of statistical parameters will follow BI standards [\(10\)](#).

Descriptive statistics for continuous variables will generally contain N (number of patients in that patient set), Mean, Standard Deviation, Minimum (Min), P25 (25th percentile), Median, P75 (75th percentile), Maximum (Max). In general, means, SDs, medians, P25 and P75 will be presented to one more decimal place than the raw data. Minima and maxima will be presented to the same number of decimal places as the raw data.

Tabulations of frequencies for categorical data will include all possible categories and will display the number of observations in a category as well as the percentage (%) relative to the respective treatment group total. Percentages will be rounded to one decimal place.

In general a category “missing” will be displayed. Percentages will also generally be based on all patients in the respective patient set whether they have non-missing values or not.

Sort order for general categorical variables: If categories correspond to the collected categories on the eCRF and the table shells do not explicitly specify the ordering, the “default ordering” defined by the eCRF is to be used in such cases. If categories are derived the ordering as specified in the table shell document should be used; in general ordinal data (e.g. categorised continuous data) are to be displayed in ascending order.

The denominator of the main categories is defined by the number of patients in the used patient set. The main categories define the denominators of the subcategories. Subcategories should be indented and “[N (%)]” to be displayed only for the main category.

If a table includes only categorical data, “[N (%)]” is to be displayed in the column header.

Abbreviations (e.g., Wors.) or acronyms (e.g., PD) should not be displayed in tables and patients data listings without any explanation. They will be either spelled out in the table or explained in footnotes (whatever is more reasonable from the programming point of view).

If applicable, conversion from days to weeks, months and years will be as follows:

- Weeks = days \div 7
- Months = $12 \times$ days \div 365.25
- Years = days \div 365.25

7.1 DEMOGRAPHIC AND OTHER BASELINE CHARACTERISTICS

Only descriptive statistics are planned for this section of the report.

7.1.1 Disposition of patients

For patient disposition the standard descriptive table from the EOT catalogue will be populated.

7.1.2 Important protocol deviations

A table and a listing of patients with important protocol deviations based on [Table 6.2: 1](#) will be created in Section 15.1.3 and Appendices 16.2.3 and 16.1.13.1.3 respectively, of the clinical trial report (CTR).

Proprietary confidential information © 2018 Boehringer Ingelheim International GmbH or one or more of its affiliated companies

7.1.3 Demographic and other baseline characteristics

Standard descriptive analysis and summary tables for all patients treated by initial treatment will be created for demographic data, oncological history and baseline conditions.

7.2 CONCOMITANT DISEASES AND MEDICATION

Only descriptive statistics are planned for this section of the report. Concomitant diseases will be coded similarly as adverse events based on the most current Medical Dictionary for Regulatory Activities (MedDRA) version. Concomitant therapies will be coded according to World Health Organisation - Drug Dictionary (WHO-DD). Concomitant therapies (CT) will be classified according to the Anatomical, Therapeutic, Chemical (ATC) classification system. The third ATC level will be used to categorise CTs by therapy type. In situations where a medical product may be used for more than one equally important indication, there are often several classification alternatives. As appropriate, patients receiving CTs with more than one possible ATC level-three category will be counted more than once; footnotes will clarify this possible double counting in tables.

Concomitant medications will be presented according to whether they are concomitant with the reception of study medication, or whether they were given prior to study medication. In case start and stop dates of the medications are completely missing, they are assigned as given prior to study medication.

7.3 TREATMENT COMPLIANCE

Compliance was not analysed separately, but assessed in terms of exposure (including dose intensity, refer to [Section 7.7](#) for further details on exposure analysis).

7.4 PRIMARY ENDPOINTS

The primary endpoints are the MTD and the occurrence of DLT. The MTD is determined from the occurrences of DLTs during the MTD evaluation period (this period is defined in [Section 5.1](#)). An overall summary of the DLTs (see CTP Section 4.1.3.2 for definitions of DLT) which occurred during the MTD evaluation period and the on-treatment period will be provided for each dose cohort.

Patients that were treated but replaced for the MTD evaluation (see CTP Section 3.3.5) will be excluded from the MTD determination. Replacement of patients will be determined on a case by case basis; exclusion of these patients from the MTD evaluation will be confirmed by the trial team at the report planning meeting prior to database lock.

A listing of patients with DLTs by initial treatment will be performed.

In case the MTD will not be reached until 1400 mg, it will be deemed as a sufficient tolerability in Japanese patients with advanced solid tumours at 1400 mg.

Proprietary confidential information © 2018 Boehringer Ingelheim International GmbH or one or more of its affiliated companies

7.5 SECONDARY ENDPOINTS

7.5.1 Key secondary endpoints

This section is not applicable as no key secondary endpoint has been specified in the protocol.

7.5.2 Other secondary endpoints

This section is not applicable as no secondary endpoint has been specified in the protocol.

7.7 EXTENT OF EXPOSURE

The variables defined in [Section 5.4.2](#) will be summarised descriptively for each dose cohort.

7.8 SAFETY ANALYSES

All safety analyses will be performed on the TS. Patients who were replaced within the first treatment cycle will be excluded from the determination of the MTD.

7.8.1 Adverse events

The analyses of AEs will be descriptive in nature. All analyses will be based on the number of patients with AEs (not the number of AEs).

For analysis multiple AE occurrence data on the CRF will be collapsed into an AE event provided that all of the following applies:

- All AE attributes are identical (Lowest Level Term (LLT), Common Terminology Criteria for Adverse Events (CTCAE) grade, action taken with trial medication, therapy

Proprietary confidential information © 2018 Boehringer Ingelheim International GmbH or one or more of its affiliated companies

required, seriousness, reason for seriousness, relationship, outcome, AE of special interest)

- The occurrences were time-overlapping or time-adjacent (time-adjacency of 2 occurrences is given if the second occurrence started on the same day or on the day after the end of the first occurrence)

For further details on summarisation of AE data, please refer to [\(2\)](#) and [\(6\)](#).

Adverse events will be coded with the most recent version of MedDRA. The severity of AEs will be scaled according to CTCAE (CTCAE version 4.03 [\(11\)](#)).

The analyses of adverse events will be based on the concept of treatment-emergent adverse events. That means that all adverse events with an onset between first treatment administration until end of the REP will be assigned as ‘on treatment’. All adverse events occurring before first drug intake will be assigned to ‘screening’ and all adverse events occurring after the residual effect period will be assigned to ‘post-treatment’; these AEs will be displayed in listings only. Adverse events will be displayed by the initial dose of Xentuzumab administered on the first day of treatment with Xentuzumab. Adverse events will be displayed by the initial dose of study medication administered on the first day of treatment

An overall summary of adverse events will be presented. The frequency of patients with adverse events will be summarised by treatment, primary system organ class and preferred term. Separate tables will be provided for patients with drug-related adverse events, adverse events leading to dose reduction, adverse events leading to discontinuation, serious adverse events, adverse events leading to death, other significant adverse events, adverse events of special interest, and adverse events fulfilling the DLT definition

Sorting order:

In tables presenting System Organ Classes (SOCs) and Preferred Terms (PTs), SOCs will be sorted alphabetically and PTs (within SOC) by descending frequency.

Reporting of CTCAE grades in tables:

In tables showing AEs by worst CTCAE grade, AEs with missing CTCAE grade will only be displayed under the category “All grades”, but no category “Missing grade” will be displayed. Therefore the categories “Grade 1” to “Grade 5” might not add up to the category “All grades”; a footnote will explain this handling.

Displaying of CTCAE grades in AE tables (Section 15) will be “All grades”, “Grade 1”, “Grade 2”, “Grade 3”, “Grade 4”, and “Grade 5” separately.

Listings of adverse events

Adverse events will be reported with start and end day as calculated from the first day of treatment with study medication.

Incidence and severity of adverse events

The incidence of AEs overall (irrespective of relatedness to study medication), related AEs, and serious AEs (SAE) will be reported by severity according to CTCAE grades.

Other significant adverse events

Proprietary confidential information © 2018 Boehringer Ingelheim International GmbH or one or more of its affiliated companies

Other significant AEs are defined as serious and non-serious AEs that lead to dose reduction or permanent discontinuation of study medication. Their incidence will be reported by severity according to CTCAE grades.

A listing of patients who developed 'other significant' AEs will be provided and a flag for serious and non-serious will be included.

AEs leading to dose reduction or permanent discontinuation will include:

- AEs leading to dose reduction of Xentuzumab
- AEs leading to permanent discontinuation of Xentuzumab

AEs leading to death

AEs leading to death during the on-treatment period will be tabulated in a separate table. In this table no CTCAE grades will be shown. For fatal AEs without CTCAE grade 5 or missing grade, the grade will be imputed as CTCAE grade 5. Reported fatal AEs that occurred in the post-treatment period will be listed within the listing containing all post-treatment AEs.

Protocol-specified Adverse Events of Special Interest (AESI)

Protocol-specified AESIs are specified in the CTP Section 5.2.2.1. Their incidence will also be reported.

